13. ETHICAL AND REGULATORY CONSIDERATIONS	
14. DISSEMINATION POLICY	
15. REFERENCES	
16. APPENDICES	

ii. LIST OF ABBREVIATIONS

Define all unusual or 'technical' terms related to the study. Add or delete as appropriate to your trial. Maintain alphabetical order for ease of reference.

AE	Adverse Event
AR	Adverse Reaction
AIR	Assessment of Injecting Risk
CA	Competent Authority
CI	Chief Investigator
CRF	Case Report Form
CTA	Clinical Trial Authorisation
CTIMP	Clinical Trial of Investigational Medicinal Product
CTU	Clinical Trials Unit
DMC	Data Monitoring Committee
DSUR	Development Safety Update Report
ECG	Electrocardiogram
GCP	Good Clinical Practice
GMP	Good Manufacturing Practice
IB	Investigator Brochure
ICF	Informed Consent Form
ICH	International Conference on Harmonisation of technical requirements for registration of pharmaceuticals for human use.
IMP	Investigational Medicinal Product
IP	Intellectual Property
ISF	Investigator Site File (This forms part of the TMF)
ISRCTN	International Standard Randomised Controlled Trials Number
KCL	King's College London
MA	Marketing Authorisation
MHRA	Medicines and Healthcare products Regulatory Agency
NHS R&D	National Health Service Research & Development
NIMP	Non-Investigational Medicinal Product
PI	Principal Investigator
PIS	Participant Information Sheet
PW	PneumoWave
PM	Project Manager
QA	Quality Assurance

QC	Quality Control
QP	Qualified Person
RCT	Randomised Control Trial
REC	Research Ethics Committee
SAE	Serious Adverse Event
SAR	Serious Adverse Reaction
SDV	Source Data Verification
SHIP	Scottish Health and Industry Partnership Group
SIRD	Substance Induced Respiratory Depression
SOP	Standard Operating Procedure
SmPC	Summary of Product Characteristics
SSI	Site Specific Information
SUSAR	Suspected Unexpected Serious Adverse Reaction
TMF	Trial Master File
TMG	Trial Management Group
TSC	Trial Steering Committee
UKCA	United Kingdom Conformity Assessed

iii. STUDY SUMMARY

Study Title	Feasibility of Virtual Safe Drug Consumption Technology, Using Respiratory Monitoring to Reduce Drug Harm	
Internal ref. no. (or short title)	RESCU-2	
Clinical Phase	Phase II	
Study Design	Observational	
Study Participants	People who use drugs living in supported accommodation	
Planned Sample Size	
Around 50 participants to use the Pneumowave DC Mobile System
 
Up to 20 participants to take part in semi-structured interviews
 
Up to 20 participants to take part in focus group(s)
 
Up to 20 site staff to take part in focus group(s)
	
Observation duration	Minimum of one night, up to 4 weeks, with a continuous option to extend for a further 4 weeks.	
Follow up duration	N/A	
Planned Study Period	
1 Year
 
6-8 months recruitment
 
4-6 months data analysis
	
	Objectives	Outcome Measures
Primary	To capture chest motion data using the PnemoWave DC Mobile system.	Evidence of reduced chest movement collected by PW DC Mobile system.
Secondary	Potential causes for Substance Induced Respiratory Depression	Participant reported drug use; drug diary, Assessment of Injecting Risk (AIR) Tool. Participant reported existing respiratory condition; CRF
Secondary	User and staff experience and acceptability.	Participant reported outcomes; participant and staff questionnaires, satisfaction survey, interviews, focus groups;
Investigational Product(s)	PnemoWave DC Mobile System	
Route of Administration	Biosensor worn on the chest, attached by ECG electrode adhesive patch. Biosensor connected via Bluetooth to a	

	Mobile Device running an App. Mobile Device is required to be connected to the internet via wi-fi or mobile data.
--	---

iv. FUNDING AND SUPPORT IN KIND

FUNDER(S) (Names and contact details of ALL organisations providing funding and/or support in kind for this trial)	FINANCIAL AND NON FINANCIAL SUPPORT GIVEN
SHIP	Financial Support
Scottish Government Office of Life Sciences	Financial Support
PneumoWave	Supply of devices and software support

v. ROLE OF STUDY SPONSOR AND FUNDER

The roles and responsibilities of the Sponsor and Funder will be detailed in the Clinical Research Agreement.

vi. ROLES AND RESPONSIBILITIES OF TRIAL MANAGEMENT COMMITTEES/GROUPS & INDIVIDUALS

The study will be coordinated by a Trial Management Group (TMG), consisting of the grant holders, including the CI, collaborators, statistician, trial manager and 3rd sector workers where appropriate. Details of membership of the TMG will be held in the Trial Master File (TMF). The TMG will meet regularly to ensure all practical details of the study are progressing well and working well and everyone within the study understands them. Minutes of the TMG meetings will be maintained in the TMF.

The functions of the Trial Steering Committee (TSC) will be undertaken by the TMG. No independent TSC or Data Monitoring Committee (DMC) will be convened for this study.

The CI will be responsible for the conduct of the study. Site delegate(s) will oversee the study and will be accountable to the CI. A study-specific Delegation Log will be prepared for the study sites, detailing the duties of each member of staff working on the study.

vii. Protocol contributors

TCTU Portfolio Trial Manager: [name], initial draft

Chief Investigator, [name], review

Principal Investigator, [name], review

TCTU Senior trial manager: [name], review

PneumoWave Clinical Research manager: [name], review

PneumoWave CSO: [name], review

King’s College London Research Associate: [name], review

King’s College London Research Fellow: [name], review

[figure not shown]
King’s College London Clinical Research Fellow: [name], review

King’s College London Lecturer: [name], review

[figure not shown]
viii. Key Words

SIRD, overdose, biosensor, respiratory rhythm, reduced chest movement, monitoring session, algorithm,

ix. STUDY FLOW CHART – LONG TERM RESIDENTS – 4 WEEKS+

x. STUDY FLOW CHART – SHORT TERM RESIDENTS

1 BACKGROUND

Opioid overdose is now the largest cause of accidental death in most developed countries. In the UK and US last year there were more than 80,000 deaths (CDC.gov, 2021). The Opioid Crisis is a public health emergency with a catastrophic socioeconomic impact (Ciccarone, 2019). All existing measures have failed to stop deaths increasing year-on-year and technology that can successfully prevent deaths by linking accurate diagnosis with rapid naloxone administration presents a very large commercial opportunity, creating multiple highly-skilled jobs, and placing the UK at the forefront of addressing the Opioid Crisis. Death from overdose is caused by opioids blocking respiratory rhythm generating centres in the brain leading to slow, irregular breathing progressing to complete cessation of respiratory effort (Palkovic, 2020). While the effect is dose related, other factors make susceptibility to overdose unpredictable. In 2019, PneumoWave conducted an Innovate UK funded project evaluating multiple sensor technologies. Accelerometers were identified as the most appropriate sensor for the purpose of overdose detection due to the robust and accurate provision of continuous longitudinal data from which conscious level and a number of features of respiration can be derived. Added benefits of accelerometers include reliability, availability, low power usage, cost, and small size. A commercially ready version of the PneumoWave biosensor is currently being used in multiple clinical studies (*RESCU*, UK and *OD-SEEN*, Australia), with positive clinician and lived-experience patient feedback, giving a high degree of confidence in suitability of the chosen sensor and device methodology.

2 RATIONALE

Recently, technological developments in wireless 'wearable' devices have enabled real-world, real-time measurement of physiological functioning. Remote measurement of respiratory, cardiovascular, and motor function has the potential to detect opioid overdose automatically and reliably (Goldfine, 2020). However, currently available wearable devices have no ability to detect respiratory depression and have limited utility for use as regulated medical devices. Existing chest-worn vital sign sensors are not practical or economically viable for individual use in the community. In addition, little research into the efficacy of remote overdose detection has been conducted. A chest sensor that reliably detects the overdose breathing signature could alert the emergency services and save lives, when fully developed and used in the community. Qualitative study results indicate that this technology would be positively accepted by people who use drugs (PWUD) (Tas, 2023).

The PneumoWave DC Mobile chest biosensor is a small cylindrical device (40mm diameter 14mm height) that sticks onto the chest using a small plastic patch (an ECG sticker) and measures chest motion. PneumoWave are developing an Alert algorithm (that will be incorporated in the DC Mobile system) that will detect reduced chest movement linked to Substance Induced Respiratory Depression (SIRD). To gather device utility and wearability feedback, and refine the Alert analysis algorithm a study is required on patients at high risk of SIRD to capture chest motion during times when possible consumption events might be occurring, where absence or presence of overdose can be externally verified.

Over a six to eight month period, we aim to capture approximately 50 participants known to use opiate drugs, including opioid injection, wearing the device for multiple nights in supported accommodation centres in the UK. Participants will consent to wear the chest-worn device during their residence at the supported accommodation. Chest motion data will be collected on the device securely and pseudo-anonymously (i.e. study ID will be used; no personally identifiable information will be stored alongside chest motion data) and streamed to a secure cloud.

The data collected here will be used to test and further develop respiratory 'signatures' to accurately detect SIRD and differentiate from patterns that occur following substance use but do not result in an overdose. Wearing the device will not alter the services participants receive at the supported accommodation.

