2.1 Assessment and management of risk

There is zero to minimal risk to participants from the biosensor itself. It may be mildly uncomfortable to wear initially but participants should soon become used to it. Several Clinical Research projects have been conducted with the technology (eg. *RESCU: RESpiratory monitoring reduCing drUg harm*, IRAS 301153) with over 150 participants and 15,000 hours of wear. No adverse events related to the biosensor have been reported.

There is no risk of personal data being revealed via the DC Mobile software. All chest movement data is anonymous.

Participants are people who actively use drugs and may be at risk of accidental overdose. Supported accommodation sites involved in the study have trained staff to administer naloxone, to reverse the effects of an opioid overdose or to administer first aid. Participants will be informed that the device will not issue an alert in the event of a potential overdose. Supported accommodation staff perform regular wellness checks on residents who show signs of drug use throughout the evening. Staff will continue to perform these checks on study participants, so there is no change to the risk of accidental overdose.

Sites provide advice and additional services to help residents stop using opiates and other drugs. Participants will not be disincentivised from using these services.

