10.3 Statistical analysis plan

A statistical analysis plan will be finalised prior to data lock.

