10.3.2 Primary outcome analysis

- Biosensor data analysed to determine whether or not an alarm would have been raised (and possibly the timing of the alarm)
- Staff measured outcomes reviewed to categorise whether there was cause for concern about the participant
- Above measures compared to determine either True Positive / False Positive / True Negative / True Positive events
- Sensitivity and Specificity are calculated for the complete data set (ideally with error bars calculated by an appropriate statistical method)

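### Section 10.3.2 scores accuracy on the complete data set without naming the algorithm version, while section 2 plans to refine the algorithm on the same recordings, so reported sensitivity is liable to be optimistic

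*Protocol*

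**What the plan says.** - **Purpose (protocol section 2).** The manufacturer's Alert algorithm is still under development. One reason given for the study is to "refine the Alert analysis algorithm a study is required on patients at high risk of SIRD". The same section says: "The data collected here will be used to test and further develop respiratory" signatures, so that overdose can be told apart from drug use without overdose.
- **Accuracy analysis (section 10.3.2).** The alarm is worked out retrospectively from the biosensor data. The reference is described as "Staff measured outcomes reviewed to categorise whether there was cause for concern about the participant". The two are cross-classified, and "Sensitivity and Specificity are calculated for the complete data set". The section names no algorithm version, threshold, freeze point, hold-out set or cross-validation.
- **SAP timing (section 10.3).** "A statistical analysis plan will be finalised prior to data lock".
- **Live alerts (section 2.1).** "Participants will be informed that the device will not issue an alert in the event of a potential overdose".
- **Who does what (sections 11.1 and 11.2).** Proprietary algorithms are applied to the respiratory data with the manufacturer's help. Data analysis is assigned to a university partner.
- **Size (section 10.1).** About 50 participants, with no sample size calculation. No number of expected events is given anywhere.

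**The concern.** An algorithm tuned on a set of events will look better on those events than on new ones, because the tuning also follows their chance features. Section 2 announces the tuning and section 10.3.2 scores all the data, so nothing in the text prevents the tuned version from being scored on the events that tuned it. The figure most exposed is sensitivity, which says how many overdoses would be missed. It rests on the events, and these may be few.

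A second route to optimism is the reference itself. Deciding whether a staff record shows cause for concern is a judgement made at analysis. If the person judging knows whether the algorithm alarmed, borderline records can drift towards agreement with it.

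At stake is a published sensitivity and specificity (section 14.1 plans publication) that readers would take as a test of the algorithm when it may be a description of its fit.

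**Working it through.** **1. The text, side by side.** Section 2 plans development on these recordings. Section 10.3.2 takes every recording for the accuracy estimate. Two cases follow:

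- The scored version was fixed without use of these data. There is then no optimism from this source, and scoring the complete data set is sound.
- The scored version was refined on these data. The estimate is then resubstitution accuracy.

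The protocol does not say which case applies. Its only timing rule is that the SAP precedes data lock. Recordings are streamed to a cloud store throughout the 6 to 8 months of recruitment, so a SAP that meets this rule could still be signed after the data had been used for tuning.

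**2. Is there a figure to reproduce?** No. The protocol states no expected accuracy, precision target or event count. What follows is illustration on assumed inputs.

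**3. Best of several settings.** Assumed: true sensitivity p = 0.70 for each of K = 10 candidate settings, n events, and the setting with the highest observed sensitivity is kept. If the settings err independently, with F the Binomial(n, p) distribution function,

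E[apparent sensitivity] = (1/n) × Σ (x = 0 to n−1) [1 − F(x)^10].

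For n = 5, F(3) = 0.4718 and F(4) = 0.8319. Their tenth powers are 0.0005 and 0.159, and the lower terms are negligible. The sum is 5 − 0.1593 = 4.841, and 4.841/5 = 0.968.

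For correlated settings, each event has a normal latent score with correlation ρ between settings and is detected when the score falls below the 70% point (40,000 simulated runs). Mean apparent sensitivity, against a true 70%:

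| Events | ρ = 0.99 | ρ = 0.95 | ρ = 0.8 | independent |
|---|---|---|---|---|
| 5 | 75% | 80% | 86% | 97% |
| 8 | 75% | 79% | 84% | 92% |
| 20 | 74% | 77% | 80% | 85% |

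On these inputs the overstatement runs from about 4 points (74 − 70) to 27 points (97 − 70). The model picks on sensitivity alone and ignores the trade-off with specificity.

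**4. A second model that includes the trade-off.** Assumed: a true separation of 1 SD, 1,000 non-event windows, feature and threshold chosen by the largest Youden index, 400 runs per setting.

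| Events | Features | Apparent sensitivity | True sensitivity | Difference |
|---|---|---|---|---|
| 5 | 1 | 0.84 | 0.61 | 0.23 |
| 5 | 5 | 0.94 | 0.55 | 0.39 |
| 20 | 1 | 0.75 | 0.65 | 0.10 |
| 20 | 20 | 0.86 | 0.60 | 0.26 |

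Specificity was overstated by 0.01 or less, because the assumed non-event windows are many. This is why the point bears mainly on sensitivity. In both models the optimism shrinks as events increase.

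**5. The reference.** Section 2.1 rules out a live alert and section 8.1 places the Alert algorithms outside the device system, for retrospective use. Staff therefore write their records without an alarm result. The categorisation in section 10.3.2 comes later, and no text keeps the alarm result from whoever does it.

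**The case against.** The strongest reply is that the protocol never says a refined version will be scored. Testing and further developing can be a sequence: test the existing signatures, then improve them. Section 8.1 describes Alert algorithms as existing. Section 2.1 reports earlier studies with over 150 participants and 15,000 hours of wear, which could have served as a separate development set, though the protocol does not say so. This stands. A reader might infer that the reported accuracy is certain to be biased, and the documents do not support that. They support only that nothing rules it out.

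A reader might also infer that the alarm result is known when staff records are judged, because the alarm comes first in the list in section 10.3.2. The bullets are unnumbered and set no order. The staff records are made without an alarm, and section 7.4 has staff note concrete facts such as the level of intervention. The analysis sits with a university partner, and section 13.7 denies the manufacturer identifiable details. That does not exclude its access to pseudonymised outcomes. What remains is narrow: the later categorisation has no stated protection.

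Version freeze and validation method are often left to a SAP, and one is promised. But the pairing of section 2 with section 10.3.2 is the protocol's own text, and so is the deadline in section 10.3, which can be met too late to help.

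Finally, this is a feasibility study whose stated objective is to capture chest motion, and no care decision depends on the estimate. That lowers the stakes. It does not remove them, since section 10.3.2 makes sensitivity and specificity the primary outcome analysis.

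**Conclusion.** The point holds in conditional form. Sections 2 and 10.3.2 together leave open that the algorithm is scored on the recordings used to refine it. If that happens, reported sensitivity is liable to be too high, and specificity much less so if non-event windows are many. The size is unknown. With an assumed true sensitivity of 70% and the best of 10 settings, the illustration gives about 75 to 97% with 5 to 8 events and 74 to 85% with 20 events, for correlations from 0.99 to independent. Every input there is an assumption. In particular, that events will be few is plausible but not stated: monitoring can run up to 8 months and no event unit is defined. If the scored version is frozen before it meets these data, the expected optimism from this source is zero. The missing protection of the outcome categorisation is a lesser, separate weakness of the same analysis.

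**What to change.** In sections 10.3.2 and 10.3, state that:

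1. The primary sensitivity and specificity are those of an algorithm version and threshold frozen before any linkage to staff outcomes.
2. Any version refined on these data is reported separately as development accuracy, with leave-one-participant-out cross-validation or, failing that, with the label of apparent accuracy.
3. The categorisation of staff outcomes is completed and locked before alarm results are linked to it, and the algorithm is run without access to staff outcomes.
4. The SAP is signed before linkage, not only before data lock.

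No further participants or recordings are needed. The cost is some extra analysis work (keeping the frozen version, arranging the categorisation, refitting for cross-validation) and a less favourable accuracy figure for the refined version. The change has to come before linkage, because a freeze cannot be recreated once the developers have seen the outcomes.

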2.1 Assessment and management of risk

There is zero to minimal risk to participants from the biosensor itself. It may be mildly uncomfortable to wear initially but participants should soon become used to it. Several Clinical Research projects have been conducted with the technology (eg. *RESCU: RESpiratory monitoring reduCing drUg harm*, IRAS 301153) with over 150 participants and 15,000 hours of wear. No adverse events related to the biosensor have been reported.

There is no risk of personal data being revealed via the DC Mobile software. All chest movement data is anonymous.

Participants are people who actively use drugs and may be at risk of accidental overdose. Supported accommodation sites involved in the study have trained staff to administer naloxone, to reverse the effects of an opioid overdose or to administer first aid. Participants will be informed that the device will not issue an alert in the event of a potential overdose. Supported accommodation staff perform regular wellness checks on residents who show signs of drug use throughout the evening. Staff will continue to perform these checks on study participants, so there is no change to the risk of accidental overdose.

Sites provide advice and additional services to help residents stop using opiates and other drugs. Participants will not be disincentivised from using these services.

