4 STUDY DESIGN

This is an observational study. It will not incorporate any randomisation or intervention. Participants' health care and the management of any potential SIRD event will not be altered by the procedures of the protocol.

People who use drugs often live in supported accommodation, either for short periods or over a period of years. Many may continue to use drugs while on these premises. To stay at these premises people must be registered as a resident. Short term residents must register before they take up accommodation. Potential participants will be opportunistically recruited by staff working in these premises who are trained to fully explain the study and take informed consent. Drug use is discussed with residents for their own safety. Accommodation staff engage regularly with this population and will be able to identify those who may be eligible. This lowers the risk of them approaching people who do not use drugs and potentially causing unintentional offence or stereotyping. Some supported accommodations will provide injecting equipment on request. This would identify a potentially eligible participant. Consented participants will be recorded on an enrolment log at each participating site. The enrolment log is for administration purposes only and will only be available to site personnel.

The study will utilise the PneumoWave DC Mobile biosensor and data collection platform which includes a wearable biosensor that attaches to the press-stud on a supplied and approved ECG electrode. The biosensor can be placed in a number of locations on the chest and diaphragm area, and automatically connects to a Data Hub via Bluetooth (Fig. 1). The position of the biosensor should be changed weekly. In this study the Hub will be a mobile computing platform (Application running on a tablet). The tablet will be held in a secure location, remaining in range of connection for the PneumoWave DC Mobile biosensor. The tablet has no functionality beyond running the monitoring app. Participants will be informed of this and the tablet's location in their residence. Please see further details in the Study Assessments section (section 7.4).

Figure 1:

Participants receive the device to wear and a tablet with the DC Mobile app downloaded to record data while they are in their accommodation. The wearable device battery will be changed 1-2 times per week.

Long term residents: monitored for 4 weeks or longer up to 8 months

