Supported accommodation staff will check in weekly with participants to ensure the device is being worn, is working and the associated tablet is also present and in a working condition. Participants will receive £25 per week if these conditions are met (further detailed in Payment section). This will encourage participants to look after the device and tablet as only a limited number of each will be available at each site. Site staff will check in on participants overnight to check the device is being

worn and the app is running and note any potential drug use. Participants will be asked to wear the device for 4 weeks initially, with an option to extend the period, if agreed. This continues until the participant declines to be part of the study any longer or the study end point is reached, whichever is first.

Short term residents: monitored overnight

Participants will receive the biosensor and tablet to use overnight and return in the morning. They will receive £5 for returning both the biosensor and device in the morning. Up to a maximum of £25. If they remain a resident, they will recollect the biosensor and tablet for all nights that they are resident. This continues until the participant declines to be part of the study any longer or the study end point is reached, whichever is first. Site staff will be trained to ask for ongoing consent if there are three or more nights where the participant has not been resident at the supported accommodation, following initial informed consent. Site staff will check in on participants to check the device is being worn and the app is running and note any potential drug use.

Applicable to all residents/participants:

It is not expected that participants will always be at a participating site. When leaving the site, the biosensor should be left behind along with the tablet. The biosensor can continue to collect chest movement data while out of range of the tablet for 10-12 hours, once back in range, data will automatically be sent to the tablet. A light on the biosensor will flash red for the duration of time it is out of range.

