6.2 Exclusion criteria

- Does not meet one or more of the inclusion criteria
- Skin sensitivity to ECG electrode patch
- Broken skin over chest area
- Implanted pacemaker device in-situ
- Not suitable for enrolment in opinion of site staff or investigators

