7.1.3 Payment

Long term resident participants will receive £25 per week dependent on evidence of wearing the biosensor and the tablet remaining in situ in their residence.

Short term participants will receive £5 for returning the biosensor and tablet the morning after use. Up to a maximum of £25.

Participants will receive £20 for taking part in semi-structured interview and £10 for participation in a focus group.

To avoid supported accommodation keeping physical money on-site, where possible participant payments will be made using the Cash Out system (<https://tinyurl.com/mr9c75kn>). This involves the supported accommodation staff sending a text message to the participant, stating the cash value to be received. This text message can be presented at any PayPoint location and the participant will receive the cash value. If a participant does not have a mobile telephone, arrangements will be made to provide the participant with the cash sum or a shopping voucher of the corresponding value.

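### For long-term residents, the cited wear experience says little about 4 weeks or more of wear, and passive event finding plus a wear-dependent payment could leave skin reactions under-reported

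*Protocol*

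**What the plan says.** **Risk statement.** Protocol 2.1 opens with "There is zero to minimal risk to participants from the biosensor itself". It rests this on earlier projects "with over 150 participants and 15,000 hours of wear. No adverse events related to the biosensor have been reported". It gives neither the spread of wear time nor the longest wear.

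**Planned wear.** Section 4 has "Long term residents: monitored for 4 weeks or longer up to 8 months". They are asked for 4 weeks first, with an option to continue. The Study Summary gives one night to 4 weeks, extendable by a further 4 weeks. Short-term residents wear the sensor overnight and hand it back each morning.

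**Skin.** Section 6.2 excludes people with "Skin sensitivity to ECG electrode patch" and people with broken skin on the chest. Section 4 has the sensor moved to a new position weekly. No later section names a skin check.

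**Contacts during wear.** In section 4, staff "check in weekly with participants to ensure the device is being worn, is working" and see that the tablet is present and working. Overnight checks cover wear, the app and signs of drug use.

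**Adverse events.** Appendix 1 collects them throughout. Section 9.2 has site staff report those directly related to wear, and section 9.3 makes device-related events a study outcome. Section 9.4 has the research team find them from what participants say in the CRF or in interviews.

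**Payment.** Section 7.1.3 states "Long term resident participants will receive £25 per week dependent on evidence of wearing the biosensor", together with the tablet staying in place. Section 4 says the same. Short-term residents are paid £5 per return of the equipment, up to £25. Interviews (£20) and focus groups (£10) are paid separately.

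**The concern.** By its own exclusions and the weekly change of position, the protocol treats the skin under the electrode as a place where the device could cause trouble. The reassurance in 2.1 comes from wear that was, on average, shorter than the wear planned for long-term residents. That would matter less if the study looked actively for skin reactions, but three features point the other way for this group:

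- Events surface mainly when a participant mentions them.
- The one regular weekly contact is about equipment.
- The participant's weekly payment depends on the sensor being worn, and nothing says what happens if it comes off because of a sore.

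At stake is a reported study outcome. With around 50 participants, device-related events are likely to be few, so one or two unreported reactions could change the picture. A clean result could then be cited for longer wear in the way that 2.1 cites the earlier projects here.

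**Working it through.** The protocol gives no hours-per-person figure, event rate or sample-size calculation to reproduce. The check compares past with planned exposure, then sets out how events would be found.

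**Inputs from the protocol:** more than 150 earlier participants, 15,000 h of wear and 0 device-related events (2.1); 4 weeks of initial wear for long-term residents (4); around 50 participants (10.2).

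**Assumption:** 8, 12 or 24 h of wear per day, because the protocol gives none. The 24 h case is an upper bound, since section 4 has the sensor left behind when participants go out.

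1. Mean earlier wear: 15,000 / 150 = 100 h per person. This equals 100 / 24 = 4.2 days of continuous wear, or about 8 to 12 nights of 12 to 8 h.
2. Planned wear over 4 weeks, compared with that mean:
   - 28 × 8 = 224 h, 2.2 times
   - 28 × 12 = 336 h, 3.4 times
   - 28 × 24 = 672 h, 6.7 times
   - For contrast, one night of 8 to 12 h is about 0.1 times.
3. Upper limit per participant at the earlier exposure (exact, one-sided 95%): 1 − 0.05^(1/150) = 2.0%.
4. Upper limit per hour: −ln(0.05) / 15,000 = 2.996 / 15,000 = 0.00020, or 2.0 per 10,000 h.
5. Upper limit over 4 weeks if the hazard is constant per hour, 1 − exp(−0.00020 × t):
   - t = 224 h: 4.4%
   - t = 336 h: 6.5%
   - t = 672 h: 12.6%
6. Sensitivity of a count in 50 people: if the true risk were 2% each, 50 × 0.02 = 1 event would be expected, and the chance of at least one is 1 − 0.98^50 = 64%. At that risk, losing a single report could turn one event into none.

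**Route by which a skin reaction becomes an event:**

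- Weekly check (section 4): wear, function and tablet. Skin is not named.
- CRF content (11.1): demographics, respiratory conditions, potential SIRD events and outcomes, and issue and return of equipment. No adverse event or skin item is listed, though the form itself is not shown.
- Satisfaction survey (7.4): at least once, on the experience of the device.
- Interviews: up to 20 participants (Study Summary), placed at end of study in Appendix 1.
- Site staff: section 9.2 expects them to report events related to wear, but the only duty section 9.4 lists for them is confirming eligibility.
- Payment (4 and 7.1.3): for long-term residents it depends on evidence of wear, with no exception for a skin problem.

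**The case against.** The strongest reply is that the protocol does provide for device-related events. They are collected throughout, site staff are to report them, they are a study outcome, and repeatable surveys invite comments on wearing the device. The CRF is not shown and may already hold a skin question. The sensor can be placed in several positions, so a sore spot need not end wear. No minimum wear is set for the weekly payment, and nothing withholds it for reporting a problem. All of this stands, and it rules out several stronger readings:

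- **That skin harm would be missed or hidden.** A reader might infer this from the payment rule and the narrow weekly check. With event collection in place, the text supports only that reactions could be under-reported.
- **That the study pays only for continued wear, for weeks to months.** This is wrong for short-term residents, who are paid for returning equipment and may wear the sensor for one night. Interviews and focus groups are also paid regardless of wear.
- **That several of the 50 will be affected, or that the limit can be carried to 8 months.** The figures are upper limits under an assumed constant hazard. They ignore the weekly change of position and are also compatible with zero events.
- **That the low-risk statement is false.** The limits concern frequency, not severity. The statement allows for minimal risk, 2.1 mentions mild discomfort, and the electrode is an off-the-shelf one. The 100 h is a mean, so some earlier participants may have worn the sensor for weeks.

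What remains is that no skin question is named after entry and no exception to the long-term payment is stated.

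**Conclusion.** The point holds for long-term residents as a weakness in how safety events are found, not as an error in a stated figure. The cited experience averages about 100 h per person, and 4 weeks of planned wear is 2.2 to 6.7 times that. Zero events in 15,000 h leaves an upper limit of 4.4% to 12.6% per person over 4 weeks. The ratio rests on the assumed 8 to 24 h per day and on treating 150 as the number of earlier participants. The limit also rests on the constant hazard, which is illustrative.

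Passive event finding and a payment tied to wear, without an exception, mean that skin reactions could be under-reported. The size of that under-reporting cannot be derived from the protocol. The primary outcome is not at issue. The change is worth making because it protects participants and the adverse event outcome at little cost.

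**What to change.** 1. In section 4, add one yes/no item with date to the weekly check (long-term residents) and to the morning return (short-term residents): any redness, itching or broken skin at the sensor site. List the item under the CRF in 11.1. Pass each positive answer to the research team as a possible device-related adverse event, and name this duty for site staff in 9.4 so that it agrees with 9.2.
2. In sections 4 and 7.1.3, state that the long-term weekly payment is not lost when the sensor is off because of a reported skin reaction at the sensor site, provided the device and tablet are present and working.
3. Optionally, in 2.1, give the earlier wear per person (mean, spread and longest) and say how much of it reached 4 weeks or more. This alone would change little.

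The cost is one item at contacts already planned and a few lines of text. The downsides are some weekly payments without full wear, some room for misuse of the exception, and, if the third change is made, a less favourable risk statement.
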